5.1.1. Intention to treat analysis and missing data

The primary statistical analysis is intention to treat including all patients randomized contributing with a full set of baseline observations. A sensitivity analysis will be done also including patients randomized with incomplete baseline observations where we may have to omit one or a few baseline covariates from the regression analyses.

Patients leaving the study completing at least three but less than six of the first six months will contribute with data up until they leave the study and this data will be extrapolated as if it was six months.. If they remained for less than three months their observations will be imputed with the mean from similar patients. Similar patients are defined as having an age of \pm five years and belonging to the same intervention group. Patients leaving during the second six months period will also contribute with data as described above.

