- 2f Phylogenetic subtype of pure cultures of E.coli in the inclusion urine culture at inclusion will be analysed in a separate statistical analysis if the number of cultures available for typing are at least 60 patients. All statistical above will be redone adding phylotype as an extra independent variable. Purely descriptive statistics will be presented in case the number is below 60.

Intention to treat analysis and missing data

The primary statistical analysis is intention to treat. Patients leaving the study completing only a part of the first six months will contribute with data up until they leave the study. Their data will be recalculated as if they had participated all six months. Patients leaving during the second six months period will also contribute with data as above. Patients leaving the study before the second six-month period commence will have their value for this period set to be the median value for both groups.

Complete case analysis

A complete case analysis will also be made where only patients having a complete data set will be included.

Per protocol analysis

A per protocol analysis will not be made.

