9. DATA MANAGEMENT

9.1. Recording of data

The investigator will ensure that all data collected in the study are recorded in a timely manner according to any instructions provided. An electronic Case Report Form (eCRF) will be used for data collection. The investigator will ensure that the data are recorded and that any corrections in the CRF as specified in the study protocol and in accordance with the instructions provided. The investigator ensures the accuracy, completeness and timeliness of the data recorded.

Research Online (RO) is an electronic data capture (EDC) system that will be used for data collection. Web-based case report forms (eCRF) are implemented into the system to facilitate the study specific data collection. These forms can easily be accessed by all standard web browsers. The baseline CRF at inclusion, telephone follow-up in case of acute UTI episode(s), telephone contact by end of treatment, telephone contact by end of study and SAE Forms will be entered onto this system. Some sites may choose to first register data in a paper version of the CRF that will later be entered into the eCRF by the coordinating centre. The investigator will sign the completed CRF. A copy of a completed paper CRF will be archived at the study site. The original paper CRF will be archived at the coordinating centre in each country.

Multiple validation and range checks will be programmed in the eCRF to assure complete and high-quality data. Data that does not comply with these rules or ranges will generate a query that must be resolved immediately or at a later stage. Electronic workflows will employ multiple skip and jump rules to ensure that only information that is applicable to the patient will appear. After the data of the last subject is entered, the clean file will be produced and thereafter the database will be closed and data made available for further analysis and publication purposes.

RO meets all requirements according to GCP standards for electronic data entry with respect to safeguarding data integrity and data security regulations. Users will have role-based access to the system by logging in using their personal username and password. The system will log all data entry steps with timestamps and user information. The role-based access to the system will avoid unauthorised data access and prevents users from performing actions that they do not have authorisation for.

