5.1.2. Complete case analysis

A complete case analysis will also be made where only randomised patients having a complete data set will be included.

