6. REASONS FOR CHANGE FROM ORIGINAL PLANNING

During discussions within the research team we have decided to make some changes to the original statistical analysis plan described in the published study protocol:

- We changed the choice of regression model from standard linear regression to negative binomial regression since the dependent variable is an integer. However, all objectives and choice of independent variables remain unchanged.
- For objective 2c the number of scale steps is only 6 and we decided ordinal regression is a better method than standard linear regression on rank transformed data.
- The statistical analysis of objective 2f was previously described as being done if we had at least 60 observations. In further discussions we decided to clarify this as including as many independent variables as possible if the condition 10 observations for each independent variable is fulfilled. This gives a structure for how to choose independent variables.
- Imputation of data in intention to treat analysis was changed for patients dropping out after participating less than 3 months. We believe it would be a better representation to use the

average from similar patients remaining in the study rather than extrapolating data from a very short time frame.

- In the original study protocol (version 11.1) we first planned an intention to treat analysis as the main analysis, a complete case analysis as a secondary analysis and that a per protocol analysis would not be made. When the study protocol was published we decided to add that a per protocol analysis will also be made (26).

All decisions above were taken before data collection were completed and before any data were analysed.

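### The SAP's primary intention-to-treat analysis leaves out randomised women with incomplete baseline data; the protocol sets no such condition and the SAP's list of changes does not record it.

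*SAP*

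**What the plan says.** **SAP 5.1.1** defines the main analysis: "The primary statistical analysis is intention to treat including all patients randomized contributing with a full set of baseline observations". It continues: "A sensitivity analysis will be done also including patients randomized with incomplete baseline observations", and adds that in this analysis "we may have to omit one or a few baseline covariates from the regression analyses". Because the remedy is to drop covariates, the baseline observations meant are the ten adjustment variables in SAP 5.1: age, urine pH, prior antibiotic courses, urease-producing bacteria, local oestrogen, diabetes, obesity, mild urogenital abnormality, sexual activity and previous urinary tract stone.

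**SAP 5.1.2** adds a complete case analysis in which "only randomised patients having a complete data set will be included".

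**Protocol 8.2** says "The primary statistical analysis is intention to treat" and then gives rules for women who leave early. It makes complete data a condition only for a separate analysis: "A complete case analysis will also be made where only patients having a complete data set will be included". It adjusts every analysis for the same ten variables but has no rule for a missing one.

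**SAP 6** lists five changes: the regression model, the method for objective 2c, the rule for objective 2f, imputation for women who leave before three months, and the added per protocol analysis. On analysis sets it says only that "we first planned an intention to treat analysis as the main analysis", with no mention of a baseline condition.

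**The concern.** An intention-to-treat analysis covers everyone randomised, in the group to which she was allocated. Under SAP 5.1.1, a woman followed for the full six months leaves the primary analysis if, for example, her BMI or her answer on sexual activity is blank. A woman who leaves before three months stays in, with an imputed outcome. The SAP thus fills in missing outcomes but discards observed outcomes when a covariate is missing.

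Three things are at stake:

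- The headline result may not describe all randomised women although its label says it does.
- Precision is lost without need, and the 25% allowance in Protocol 8.1 covers loss to follow-up only.
- The planned supporting analyses give limited help. The complete case analysis makes the same exclusion and so cannot test it. The sensitivity analysis does restore the women, but its covariates are settled only once it is known which items are incomplete.

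**Working it through.** **1. The texts side by side**

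| Place | Who is in the analysis |
|---|---|
| Protocol 8.2, primary | Intention to treat, no baseline condition stated |
| Protocol 8.2, complete case | Complete data only |
| SAP 5.1.1, primary | Randomised and full baseline data |
| SAP 5.1.1, sensitivity | Adds women with incomplete baseline data; some covariates may be dropped |
| SAP 5.1.2, complete case | Complete data only |
| SAP 6, five listed changes | Baseline condition not among them |

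**2. The plan's own sample size (Protocol 8.1)**

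Inputs: means 2.0 and 1.5, SD 1.5, two-sided alpha 0.05, power 0.80. The effect size is d = 0.5/1.5 = 0.333.

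- t-test (noncentral t): 142.2, so 143 per arm. The plan says 143.
- Mann-Whitney, relative efficiency 3/π: 142.2 × π/3 = 148.96, so 149 per arm. The plan says 149.
- With 25% loss: 298/0.75 = 397.3. The plan says at least 397, with an aim of 400.

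The figures reproduce. None of them allows for incomplete baseline data.

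**3. How many women would be excluded**

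No missingness rate is given, so the rate p per covariate is an assumption. With k covariates missing independently:

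- Excluded share = 1 − (1 − p)^k
- Interval widening = 1/√(1 − excluded)
- Power: noncentral t, d = 1/3, with n per arm = base × 0.955 × (1 − excluded). The factor 0.955 (3/π) puts it on the Mann-Whitney basis.

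Two bases are used. A base of 200 per arm treats every woman who leaves early as fully informative, because the SAP extrapolates or imputes her outcome. A base of 149 per arm treats the full 25% as lost. They are the two bounds.

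Ten covariates:

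| p | Excluded | Left of 400 | Wider CI | Power, base 200 | Power, base 149 |
|---|---|---|---|---|---|
| 0 | 0 | 400 | 0 | 90.1% | 80.0% |
| 0.5% | 4.9% | 380 | 3% | 88.7% | 78.0% |
| 1% | 9.6% | 362 | 5% | 87.1% | 75.9% |
| 2% | 18.3% | 327 | 11% | 83.5% | 71.6% |
| 3% | 26.3% | 295 | 16% | 79.6% | 67.1% |

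Eight covariates, if age and prior courses are never missing:

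| p | Excluded | Power, base 200 | Power, base 149 |
|---|---|---|---|
| 0.5% | 3.9% | 89.0% | 78.4% |
| 1% | 7.7% | 87.7% | 76.8% |
| 2% | 14.9% | 85.0% | 73.3% |
| 3% | 21.6% | 82.0% | 69.8% |

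Complete overlap: if all missing items fall in the same women, p = 3% excludes 3%. Power is then about 89% (base 200) or 79% (base 149).

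**4. Bias**

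A negative binomial simulation used means 2.0 and 1.5 (true rate ratio 0.75), SD 1.5, N = 400 and 298, and 300 runs per setting. Covariates were missing at random at 1% to 3%. The mean rate ratio was 0.745 to 0.753, both with complete-baseline women only and with mean-imputed covariates. No bias was seen. The simulated covariates were not prognostic, so this is a limited check.

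**The case against.** **The protocol may imply the same exclusion.** It adjusts for the same ten variables and has no rule for a missing one, so most regression software would drop these women. The SAP may only make that explicit. This is fair as history, but the SAP is where the gap should be closed, and it closes it by exclusion while keeping the intention-to-treat label.

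**The change list has another comparator.** SAP 6 introduces its list as changes from the published study protocol, which is not among the documents reviewed. That paper may already contain the condition. This limit stands. Protocol version 11.1, which the bullet on analysis sets names, does not contain it, and no bullet records it.

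**A sensitivity analysis is already planned.** It is, it is openly stated, and blinded analysts have little scope to steer it. It is still not the headline result, and no rule says which covariates may go.

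**The loss may be small.** Age and recent UTI episodes are needed for eligibility. Visit 1 is done by trial team members or specially trained investigators (Protocol 3.4), queries are issued (Protocol 9.2), and "Multiple validation and range checks will be programmed in the eCRF to assure complete and high-quality data". If only five items were ever missing, at 1% each, 1 − 0.99^5 = 4.9% would be excluded and power from 200 per arm would be 88.7% against 90.1%. This stands, and the upper rows of the tables should not be read as a forecast. Against it, Protocol 9.1 lets queries be resolved later and lets sites start on paper forms, and the SAP itself foresees incomplete baseline data.

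**Conclusion.** The point holds and should be fixed. The SAP's primary set is not all randomised women, the current protocol states no such restriction, and SAP 6 does not record it. This follows from the texts and needs no assumption.

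The size does depend on assumptions. At 0.5% to 1% missing per covariate, independently, 4.9% to 9.6% of women are excluded, and power falls by about 1 to 3 points from 200 per arm or 2 to 4 points from 149 per arm. The larger losses need 2% to 3% independent missingness in every item and are likely an upper range; with complete overlap the loss is about one point. No bias between arms is shown or claimed. The case rests on the definition of the analysis set and on outcomes discarded without need, more than on the power figures.

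**What to change.** - **SAP 5.1.1:** define the primary analysis set as all randomised women in their allocated group, whether or not baseline data are complete.
- **Missing baseline covariates:** prespecify single imputation that uses neither arm nor outcome: the overall mean for age, pH and prior courses, and the overall proportion for yes/no items. Use a separate missing category only where enough women lack the item, for example at least 5% (0.05 × 400 = 20 women). That cut-off is a suggestion and does not come from the documents.
- **Sensitivity analysis:** make the complete-baseline analysis the sensitivity analysis, with the same ten covariates.
- **SAP 6:** add one line recording the change.

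The cost is SAP wording and a few lines of code, with no new data. The downside is a little extra analysis work and a simple imputation assumption for the covariates. If few items are missing, the result will hardly change.

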2d	To investigate if methenamine hippurate can reduce duration of UTI episodes.	Registration of number of days of symptoms during UTI episodes.	After six months of treatment.

2e	To investigate if number of complications such as pyelonephritis and hospital admission for UTI differ between methenamine hippurate and placebo.	Registration of number of pyelonephritis and hospital admission for UTI.	Six and 12 months after commencing treatment.
2f	To investigate if phylogenetic subgroups of E. coli found at inclusion is an effect modifier in the above outcomes.	(see above)	(see above)

[figure not shown]

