5. STATISTICS

5.1. Statistical analysis

It is the intention to adjust all analysis for the following confounding variables obtained at visit 1

- patient's age
- urine acidity (pH)
- number of antibiotic courses for UTIs in the 12 months preceding inclusion in the study
- presence of urease/stone-producing bacteria in urine culture day 1 such as *proteus*, some *klebsiella* species, *Morganella morganii*, *Corynebacterium urealyticum* and *providencia*
- use of local oestrogen
- patient has diabetes mellitus
- obesity defines as BMI ≥ 30
- presence of known mild abnormality of the urogenital tract
- if the patient is sexually active.
- If the patient previously have experienced urinary tract stone

Phylogenetic subtype of pure cultures of *E.coli* in the urine culture at inclusion will be analysed in a separate analysis if the number of cultures available for typing are not too small.

The statistical calculation relates to the study objectives described in section “2 Study Objectives and Endpoints”:

- 1 Negative binomial multivariable regression will be used where number of UTI antibiotic treatments will be the dependent variable. Group allocation together with the confounding variables above will be independent variables. Histograms of the dependent variable will determine if we need to adjust for zero inflation (or any other inflation).
- 2a Will be analysed using the same statistical approach as objective 1 above.
- 2b Will be analysed using the same statistical approach as objective 1 above. Number of UTIs will be the dependent variable.
- 2c The outcome variable is measured at first day of a UTI using a six grade ordinal scale. The median value from all UTIs will be used if the patient has more than one episode of UTI. Data will be analysed using ordinal multivariable logistic regression.
- 2d Will be analysed using the same statistical approach as objective 1 above. Number of days with symptoms will be the dependent variable. The median value from all UTIs will be used if the patient has more than one episode of UTI.
- 2e Will be analysed using the same statistical approach as objective 1 above. Number of severe events such as pyelonephritis or hospital admission will be the dependent variable.

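### The primary analysis fills in patients who leave before month 3 with a same-arm mean and treats it as observed, so the standard error is too small and the type I error exceeds 5%

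*SAP*

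**What the plan says.** The primary analysis is intention to treat (SAP 5.1.1). A patient who completes three to six months has her count scaled up to six months. For those who leave sooner: "If they remained for less than three months their observations will be imputed with the mean from similar patients". Donors are patients in the same arm whose age differs by no more than five years. Section 6 explains that this was preferred "rather than extrapolating data from a very short time frame".

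The model is in SAP 5.1: "Negative binomial multivariable regression will be used where number of UTI antibiotic treatments will be the dependent variable". Section 6 gives the reason for changing to "negative binomial regression since the dependent variable is an integer".

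The rule reaches beyond objective 1. Objectives 2a, 2b and 2e use the same approach, and for the second half-year: "Patients leaving during the second six months period will also contribute with data as described above". Objective 2e is evaluated at "Six and 12 months after commencing treatment". Objective 2d also follows objective 1, but its outcome is a duration per episode: "Number of days with symptoms will be the dependent variable. The median value from all UTIs will be used".

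A complete case analysis is planned in addition, "where only randomised patients having a complete data set will be included". SAP sections 5 and 6 mention no offset for follow-up time, no multiple imputation, no robust or bootstrap variance, and no rounding of imputed values.

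**The concern.** An imputed same-arm mean carries no information about the treatment difference beyond what the donors already supply. The model nevertheless counts that patient as a full observation, and one that sits almost exactly on her arm's average. The apparent sample size rises and the apparent variance falls, so the interval is too narrow and the p-value too small. The events the patient actually had before leaving are discarded.

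This affects the trial's primary test and its confidence interval. There is also an internal inconsistency: the model was chosen because the outcome is an integer, yet both the imputed means and the scaled-up counts are generally not integers.

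**Working it through.** **Inputs from the protocol.** Section 8.1 gives means of 2.0 (control) and 1.5 (active), SD 1.5 in each arm, two-sided 5% level, 80% power, a 25% allowance for loss, and a target of 400 patients. Section 5.1 gives 200 treatment sets per arm.

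**The protocol's own figure.** The effect size is 0.5/1.5 = 0.33. The t-test needs 142.2, so 143 per arm (286). Dividing 142.25 by the Mann-Whitney efficiency 3/π gives 148.96, so 149 per arm (298). Then 298/0.75 = 397.3. The stated 286, 298 and 397 are reproduced (397.3 rounds up to 398, which the target of 400 covers).

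**Closed form.** Let a fraction f of each arm of size n be set to the arm mean.
- True variance of the arm mean: σ²/[n(1−f)].
- Variance the model reports: about (1−f)σ²/n.
- Ratio of model SE to true SE: about 1−f.
- Type I error: 2[1−Φ(1.96(1−f))].

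For f = 12.5%, 1.96 × 0.875 = 1.715, which gives 8.6%. If all of the 25% left early, 1.96 × 0.75 = 1.47, which gives 14.2%.

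**Simulation of the SAP rule.** The negative binomial dispersion is (SD² − mean)/mean². Mean 2.0 gives (2.25 − 2.0)/4 = 0.0625. Mean 1.5 gives (2.25 − 1.5)/2.25 = 0.333. There were 200 patients per arm, no treatment effect, 6,000 runs per scenario (Monte Carlo error 0.3-0.4 points) and a Wald test at 1.96. Assumptions: non-informative leaving, leaving times uniform within months 0-3 and 3-6, age equal to 70 plus a gamma variable with mean 8, and no rounding.

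| Left before month 3 | 0% | 2.5% | 5% | 6.25% | 12.5% |
|---|---|---|---|---|---|
| Closed form | 5.0% | 5.6% | 6.3% | 6.6% | 8.6% |
| Simulated, mean 2.0, SD 1.5 | 5.4% | 5.9% | 6.3% | 7.2% | 8.8% |
| Simulated, mean 1.5, SD 1.5 | 4.9% | 6.1% | 6.1% | 7.0% | 10.0% |

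The early shares are assumptions: 25% loss with none early; 10% loss with a quarter or half early; 25% loss with a quarter or half early.

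- *Standard errors at 12.5% early.* The mean model SE was 0.072 against a true SD of 0.082 (ratio 0.88), and 0.094 against 0.111 (ratio 0.85). The closed form predicts 0.875.
- *Alternatives on the same data.* A log(time) offset gave 4.8-5.6%. Extrapolation with early leavers removed gave 4.6-5.6%. Complete case gave 4.5-5.6%. The scaling of month 3-6 leavers is therefore not the source of the inflation.
- *Ten covariates, as the SAP specifies (3,000 runs; means 2.0 and 1.5).* At 12.5% early, 8.4% and 9.9% (offset 5.0% and 5.9%). At 5% early, 5.8% and 7.0% (offset 4.7% and 5.8%).
- *Separately programmed simulation, mean 2.0, without the month 3-6 scaling.* With SD 1.5: 6.2-6.9% at 5.5% early and 7.8-8.5% at 12.5%. With SD 2.0: 7.5% and 10.2%. A sandwich SE did not cure it (8.8-9.7% at 12.5% early). Shorter repeat runs (1,500-3,000) gave 5.4-7.8% at 5-6.25% early and 7.7-10.0% at 12.5%.
- *Rounding the imputed value.* At mean 2.0 this gave 5.1-5.7%. At mean 1.5 it gave 7.5 / 8.1 / 10.0 / 17.2% for 2.5 / 5 / 6.25 / 12.5% early.
- *Objective 2e at 12.5% early (4,000 runs).* The documents give no event rate, so means of 0.05 / 0.1 / 0.2 per six months and dispersion 1.0 were assumed. The SAP rule gave 6.3 / 7.9 / 9.9%; the offset gave 3.6 / 4.4 / 5.4%.

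**The case against.** The strongest reply concerns size, not mechanism.

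- **The early share is unknown and may be small.** The 25% is a planning allowance for total loss. Protocol 4.4.1 keeps patients who stop study drug under follow-up unless they withdraw consent, and section 3.4 adds calls every 30 days. This stands: the inflation could be negligible. However, the SAP wrote a rule specifically for these patients, and a primary test should keep its size whatever their number. The GP record check in section 3.4 is described as a validation of episode counts; the SAP does not say that it replaces missing follow-up.
- **The upper figure is not the protocol's null.** With no effect, the protocol's control mean implies 2.0 in both arms, where 12.5% early gives 8.8%. The 10.0% comes from a common mean of 1.5. This is fair, and the table shows both.
- **At about 5% early the excess is modest.** At mean 2.0 it is 6.3% against 5.4% with nobody early, and the adjusted run gives 5.8% against 4.7% for the offset. At 5.5% early the closed form changes the conclusion only when the correct p-value lies between 0.050 and 0.064. This stands.
- **Rounding might be intended.** At mean 2.0 it removes the inflation. The 17.2% arises with the mean exactly on a rounding boundary and is not typical, but means of 1.75 and 1.3 still gave 8.1% and 10.2% at 12.5% early. Rounding is not dependable.
- **Complete case is already planned.** It would expose a discrepancy, but it is not the primary analysis.
- **The extrapolation need not go on type I error grounds.** This is correct. The offset replaces it for coherence: it keeps integer counts and makes the same constant-rate assumption.

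**Conclusion.** The concern holds and should be fixed. Followed as written, with imputed values unrounded, the primary analysis understates its standard error by roughly the fraction imputed. Type I error is about 6-7% with 5-6% of patients leaving before month 3 and about 8-10% with 12.5%. The lower ends belong mainly to the protocol's null mean of 2.0.

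Confidence in the mechanism is high, because algebra and simulation agree. The size in this trial rests on an early share that the documents do not give, and on non-informative leaving. Informative leaving would add bias, which was not examined here.

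**What to change.** Before unblinding, amend SAP 5.1 and 5.1.1:

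- **Objective 1.** Model each randomised patient's observed count over days 2-180, with log(follow-up days) as an offset. Drop the mean imputation and the scaling to six months. This also meets the worry in SAP section 6, because a short follow-up then carries little weight.
- **2b and 2e.** Use the same offset, over days 2-180 for 2b and over each of the two windows for 2e.
- **2a.** Use the offset over months 7-12. Patients with no follow-up in that period cannot enter (log 0), and the SAP has no clear rule for them; protocol 8.2 used a median pooled over both arms. Include them by multiple imputation as a sensitivity analysis.
- **2d.** Do not impute a mean. A follow-up offset does not suit a median duration per episode, so analyse patients with an observed episode.
- **Reporting.** State whether GP-record counts serve as follow-up for patients no longer reached by telephone. Give the number leaving before month 3 in each arm. Keep the complete case analysis as a check, since the offset also assumes a constant rate and non-informative leaving.

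The cost is SAP wording and one model term. Leaving dates are already needed for the scaling rule. The interval becomes wider and correctly sized. At the protocol's effect (2.0 against 1.5, SD 1.5; 4,000 runs):

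| Loss, half of it early | Offset: power / coverage of 95% interval | SAP rule: power / coverage |
|---|---|---|
| 25% | 87.4% / 94.4% | 90.5% / 90.3% |
| 10% | 89.8% / 94.4% | 91.0% / 93.1% |

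The apparent loss of power is 3.1 points (90.5 − 87.4) and 1.2 points (91.0 − 89.8), and power stays above the planned 80%.
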